Appendix D. Administration of study drugs and placebos

Timing of administration of study drugs during pregnancy

Weeks of gestation	3 dose SP (treatment arm A)	3 dose DP (treatment arms B+C)	Monthly DP (treatment arms D+E)
16	DP placebo + SP placebo	DP placebo + SP placebo	DP + SP placebo
20	SP + DP placebo	DP + SP placebo	DP + SP placebo
24	DP placebo + SP placebo	DP placebo + SP placebo	DP + SP placebo
28	SP + DP placebo	DP + SP placebo	DP + SP placebo
32	DP placebo + SP placebo	DP placebo + SP placebo	DP + SP placebo
36	SP + DP placebo	DP + SP placebo	DP + SP placebo
40	DP placebo + SP placebo	DP placebo + SP placebo	DP + SP placebo

Timing of administration of study drugs during infancy

Weeks of age	3 monthly DP (treatment arms A+B+D)	Monthly DP (treatment arms C+E)
8	DP	DP
12	DP placebo	DP
16	DP placebo	DP
20	DP	DP
24	DP placebo	DP
28	DP placebo	DP
32	DP	DP
36	DP placebo	DP
40	DP placebo	DP
44	DP	DP
48	DP placebo	DP
52	DP placebo	DP
56	DP	DP
60	DP placebo	DP
64	DP placebo	DP
68	DP	DP
72	DP placebo	DP
76	DP placebo	DP
80	DP	DP
84	DP placebo	DP
88	DP placebo	DP
92	DP	DP
96	DP placebo	DP
100	DP placebo	DP
104	DP	DP

Appendix E. Weight-based dosing guidelines for DP during infancy

Weight (kg)	Dihydroartemisinin-Piperaquine (20mg/160mg tabs) monthly dosing given once a day for 3 consecutive days		
	Day 1	Day 2	Day 3
< 5.9	½ tab	½ tab	½ tab
6.0-10.9	1 tab	1 tab	1 tab
11.0-14.9	1 ½ tab	1 ½ tab	1 ½ tab
15.0-19.9	2 tabs	2 tabs	2 tabs
20.0-23.9	2 ½ tab	2 ½ tab	2 ½ tab
24.0-25.9	3 tabs	3 tabs	3 tabs

Appendix F. WHO Criteria for Severe Malaria and Danger Signs

Criteria for severe malaria

Cerebral malaria - defined as unarousable coma not attributable to any other cause in a patient with falciparum malaria

Generalized convulsions (≥ 3 convulsions over 24 hours period)

Severe normocytic anemia (Hb < 5 gm/dL)

Hypoglycemia

Metabolic acidosis with respiratory distress

Fluid and electrolyte disturbances

Acute renal failure

Acute pulmonary edema and adult respiratory distress syndrome (ARDS)

Circulatory collapse, shock, septicemia ("algid malaria")

Abnormal bleeding

Jaundice

Danger signs (in children only)

Less than 3 convulsions over 24 hour period

Inability to sit up or stand

Vomiting everything

Unable to breastfeed or drink

Lethargy

Appendix G. Uganda Ministry of Health Guidelines for Routine Care of Pregnant and Postpartum Women, and Newborns

In addition to receiving medical care as described above in the protocol, women and infants enrolled in the study will receive standard routine prenatal and postpartum care according to Uganda Ministry of Health guidelines. These standard procedures are subject to availability at Tororo District Hospital.

Routine antenatal care. Women enrolled in the study will receive routine care as designated in the Uganda Ministry of Health Guidelines. Routine antenatal care includes screening and treating for syphilis and syndromic management of sexually transmitted infections (STIs). Pregnant women will receive iron and folic acid supplementation. In addition, women will be given multivitamins that will be given once daily. In addition, women receive mebendazole 500mg as a single dose as early as possible after the 1st trimester. Each antenatal visit also includes blood pressure assessment and urine dip stick for proteinuria.

Routine intrapartum/delivery care. Routine delivery care for in-hospital births will include labor management by the midwifery staff and management of obstetrical complications as per Ministry of Health guidelines. Immediate postpartum infant care will include polio and BCG immunization, ophthalmic tetracycline, and vitamin K.

Routine postpartum care. All postpartum women will receive vitamin A supplementation (200,000 IU) immediately following delivery. Depending on clinical circumstances and based on local standard of care, women may receive 2 weeks of multivitamins twice a day. Common indications for postpartum multivitamins include anemia, postpartum hemorrhage and prolonged labor. Women will be seen at 1 week after delivery as per Ugandan standards of care. Women also undergo a 6 weeks postpartum visit as part of routine care. These visits include an abdominal exam, syndromic management of STIs, and follow-up on any obstetrical complications that occurred. In addition, women receive vitamin A at this visit, if not given immediately postpartum, and are continued on iron and folic acid supplementation. Pelvic and breast exam will be done if clinically indicated. Contraceptive counseling is performed at this visit as is a nutritional assessment and infant feeding and support. Screening for cervical cancer will be performed postpartum by clinical TDH staff if available at Tororo District Hospital.

Routine infant care. Infants will be referred to the TDH antenatal clinic for routine immunizations at 6 weeks, 10 weeks, 14 weeks, 6 and 9 months of life.

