6.2. Diagnosis and Management of Malaria

Patients found to have malaria based on laboratory confirmation will have a second finger prick for a thin smear (to determine parasite species), hemoglobin measurement using a portable spectrophotometer (HemoCue), and collection of plasma for future PK studies. All episodes of malaria will be classified as uncomplicated or complicated based on the following criteria:

Uncomplicated malaria (all of the following)

- 1) Fever ($\geq 38.0^{\circ}\text{C}$ tympanic) or history of fever in the previous 24 hours
- 2) Positive thick blood smear
- 3) Absence of complicated malaria

Complicated malaria (any of the following)

- 1) Evidence of severe malaria (Appendix F) and parasitemia
- 2) Danger signs present in children (Appendix F) and parasitemia

Episodes of malaria will also be classified into the following categories according to the timing of previous malaria episodes for treatment purposes:

1. New episodes of malaria will be defined as any first episode or any episode occurring > 14 days after the diagnosis of a previous episode
2. Treatment failures will be defined as any of the following:
 - a. Complicated malaria occurring 1-14 days after the diagnosis of a previous episode
 - b. Fever ($\geq 38.0^{\circ}\text{C}$ tympanic) or history of fever in the previous 24 hours with a parasite density \geq the parasite density of an episode of malaria diagnosed 2 days prior

- c. Fever ($\geq 38.0^{\circ}\text{C}$ tympanic) or history of fever in the previous 24 hours with a parasite density $\geq 25\%$ of the parasite density of an episode of malaria diagnosed 3 days prior
- d. Fever ($\geq 38.0^{\circ}\text{C}$ tympanic) or history of fever in the previous 24 hours with a positive thick blood smear of any parasite density occurring 4-14 days after the diagnosis of a previous episode

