8.2.1. Primary Outcome

The primary outcome will be the incidence of malaria, defined as the number of incident episodes per time at risk. Incident cases will include all treatments for malaria not preceded by another treatment in the previous 14 days. Time at risk will begin at birth and will end when study participants reaches 24 months of age, when the intervention will be stopped, or early study termination (if prior to 24 months of age).

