8.2.2. Secondary Outcomes

Secondary outcomes are summarized in Table 8 below.

Table 8. Secondary outcomes

Secondary outcome	Definition
Incidence of complicated malaria	Any treatment for malaria meeting criteria for severe malaria or danger signs
Incidence of hospital admissions	Admission to the pediatric ward for any cause
Incidence of adverse event	Adverse events stratified by type, severity score and relationship to study drugs
Prevalence of anemia	Proportion of routine hemoglobin measurements < 10 g/dL & < 8 g/dL
Prevalence of asymptomatic parasitemia	Proportion of routine samples (PCR or blood smears) positive for asexual parasites.
Prevalence of gametocytemia	Proportion of routine blood smears positive for gametocytes.

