8.3.1. Primary Outcome

The primary outcome will be the incidence of malaria, defined as the number of incident episodes per time at risk. Incident cases will include all treatments for malaria not preceded by another treatment in the previous 14 days. For hypothesis 3A, time at risk will begin at birth and will end when study participants reaches 24 months of age or early study termination (if prior to 24 months of age). For hypothesis 3B, time at risk will begin at 24 months of age and will end when study participants reaches 36 months of age or early study termination (if between 24-36 months of age).

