8.3.2. Secondary Outcomes

The incidence of complicated malaria will be included as a secondary outcome for both hypothesis 3A and 3B.

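### A danger sign with no age qualifier lets infants too young to sit meet the complicated-malaria endpoint by age alone, in conflict with section 6.2

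*Protocol*

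**What the plan says.** - **The sign.** Appendix F gives a list of danger signs restricted to children. One entry is "Inability to sit up or stand". It carries no lower age limit and does not ask whether the child could do this before the illness.
- **The case definition.** In section 6.2 one limb is enough for complicated malaria: "Danger signs present in children (Appendix F) and parasitemia". Uncomplicated malaria needs three conditions, the last being "Absence of complicated malaria". The schema at the front of the protocol uses the same structure.
- **The endpoint.** Table 8 in section 8.2.2 defines complicated malaria for hypothesis 2 as "Any treatment for malaria meeting criteria for severe malaria or danger signs". Section 8.3.2 adds, without a definition of its own: "The incidence of complicated malaria will be included as a secondary outcome for both hypothesis 3A and 3B".
- **The window.** For hypothesis 2: "Time at risk will begin at birth and will end when study participants reaches 24 months of age". Likewise: "For hypothesis 3A, time at risk will begin at birth". Hypothesis 3B runs from 24 to 36 months.
- **A passage that points the other way.** Section 6.2 also gives a separate treatment rule for uncomplicated malaria in children under 4 months of age or below a stated weight. It therefore takes for granted that uncomplicated malaria exists at that age.

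**The concern.** A healthy infant of a few months cannot sit or stand. If the item is scored as printed, a treated smear-positive episode at that age is complicated however mild it is, and the endpoint partly becomes a count of all malaria in early infancy.

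That matters because the two outcomes can give different answers. In the earlier Tororo treatment trial described in section 1.2, the incidence rate ratio for DP against AL was 0.85 for all malaria treatments and 0.12 for complicated malaria. Adding ordinary episodes to the complicated count pulls its contrast towards the contrast for all malaria. If clinicians read the item differently from one another, the endpoint also varies with the reader. The classification is made at the visit, so a later analysis can separate such episodes only if the qualifying sign was recorded.

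**Working it through.** **1. The passages side by side.** The protocol states no rate or power for complicated malaria (Table 10 covers primary outcomes only), so there is no figure to reproduce. The check is first one of definitions.

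| Age | Appendix F with the complicated limb of 6.2, as written | Rule for young infants in 6.2 |
|---|---|---|
| Under 4 months | The sign is present by age, so every episode is complicated | Uncomplicated malaria is expected |
| 4 months to sitting | The sign is present by age | Silent on how to score the item |
| After sitting | The sign marks illness | No conflict |

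The first row is a contradiction. The second is a gap that the under-4-months rule does not close.

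**2. Ceiling under the literal reading.** Inputs:
- 90 infants on 3-monthly DP, the control group of hypothesis 2 (Table 10).
- Sitting at about 26 weeks. This is an assumption; the documents give no age.
- A start at week 8, the first dosing visit in Appendix D. Weeks 0 to 8 are left out because section 1.1 describes newborns as protected.
- Incidence of 3 to 5 episodes per person-year, the planning range in Table 10, with 1 as an assumed low value.

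Person-time = 90 × (26 − 8)/52 = 31.2 years. Episodes = 31.2 × 1, 3, 5 = about 31, 93 and 156.

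**3. Why this is a ceiling.** The planning range is an average for 0 to 24 months, applied flat to the youngest ages. Section 1.1 says early protection wanes only after about 2 to 3 months. Section 1.2 reports incidence rising with age in all four arms of the earlier chemoprevention trial, although it also reports more than 5 episodes per year at 4 to 5 months before randomization. In this trial the 3-monthly group receives DP at weeks 8 and 20 (Appendix D). Section 1.2 gives a risk of recurrent malaria below 5% within 28 days of DP treatment. If that carried over to chemoprevention (assumption), 8 of the 18 weeks would be nearly event-free:
- Remaining 10 weeks: 90 × 10/52 × 3 and 5 = 52 and 87.
- Protected weeks: at most 90 × 2 × 5% = 9.
- Total: at most about 61 to 96, against 93 to 156.

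**4. Sensitivity to the age of sitting (m, in months).** At 3 to 5 episodes per person-year, from 2 months of age, 90 × (m − 2)/12 × rate gives 45 to 75 for m = 4, 90 to 150 for m = 6, and about 158 to 263 for m = 9. The pre-sitting period is m/24 of the 0 to 24 month window: 17%, 25% and 38%.

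**5. What relabelling does to a rate ratio.** This illustration borrows 0.12 for genuine and 0.85 for relabelled episodes from the earlier treatment trial. The genuine control-arm counts are assumptions.
- 10 genuine, 93 relabelled: (10 × 0.12 + 93 × 0.85)/103 = 0.78.
- 20 genuine, 31 relabelled: (20 × 0.12 + 31 × 0.85)/51 = 0.56.
- 5 genuine, 156 relabelled: (5 × 0.12 + 156 × 0.85)/161 = 0.83.

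The direction is the point. The values hold only if every episode is scored literally.

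**The case against.** The strongest reply is that nobody would score normal development as a danger sign. The list is applied by study physicians to sick children, and the under-4-months rule in section 6.2 shows that the authors expected uncomplicated malaria in infants who do not yet sit. This stands as evidence of intent. A reader might infer from Appendix F that every smear-positive fever in such an infant will be labelled complicated, that the uncomplicated category is empty at that age, or that misclassified episodes will dominate the endpoint. The documents do not support those statements. They describe the printed rule taken alone, and section 6.2 contradicts it. The reply does not settle the matter, because no text says when the item begins to apply and nothing covers 4 months to sitting.

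A second reply is that study drug is double-blind (section 5.4) and all arms share one standardized record form (section 7.1.2), so a misreading should follow the same rule in every arm. That also stands: no differential ascertainment is shown. It does not remove the dilution in step 5, since relabelled episodes follow each arm's incidence of all malaria.

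Third, the consequence is limited. The primary outcomes of hypotheses 2 and 3 count all malaria treatments whatever their severity, and the primary outcome of hypothesis 1 is placental. No power statement rests on complicated malaria. This stands in full.

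**Conclusion.** The point holds as a defect of definition. An unqualified item in Appendix F, carried into the endpoint through section 6.2 and Table 8, makes infants too young to sit complicated by age alone, and this conflicts with another rule in section 6.2. It is a stated rule that is too wide, not a detail left for an analysis plan.

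Its reach is the secondary outcome of complicated malaria in hypotheses 2 and 3A. Hypothesis 3B, at 24 to 36 months, is practically untouched. The figure of 31 to 156 episodes in 90 infants is a ceiling that rests on the literal reading, sitting at about 26 weeks and flat incidence of 1 to 5 per person-year. Allowing for the two DP courses lowers the 93 to 156 part of that range to at most about 61 to 96. The number that would actually be misclassified depends on how clinicians read the item, and the documents do not allow it to be estimated.

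**What to change.** In Table 8 and section 8.3.2 only, state that for the complicated-malaria endpoint this item counts only as loss of a previously acquired ability to sit or stand. Record which severe-malaria criterion or danger sign qualified each complicated episode. The case record form is not shown and may already capture this; if so, a line naming the field is enough.

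The endpoint wording should stay out of Appendix F, because that list also drives clinical classification. Appendix F and section 6.2 contradict each other on infants who do not yet sit, and the same label enters treatment-failure rule 2a and the treatment pathway in section 6.2. The clinical team must reconcile those passages; no clinical rule is proposed here.

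The cost is one sentence in each of two places and at most one field on the form. No visit, sample or procedure is added.

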Appendix H. Schedule of routine assessments and procedures in pregnant women

Evaluations and Interventions	Enrollment	Weeks of gestation							Delivery	1 and 6 weeks postpartum
		16*	20	24	28	32	36	40		
Informed consent	X									
HIV testing ¹	X				X				X	
Pregnancy confirmation ²	X									
Obstetrical ultrasound ³	X									
Blood collected by phlebotomy for CBC, ALT, and immunology studies	X		X		X			X	X	
Blood collected by finger prick for dried blood spot and plasma	X	X	X	X	X	X	X	X	X	
Routine assessment in the study clinic ⁴	X	X	X	X	X	X	X	X		X
Administration of study drugs		X	X	X	X	X	X	X		
Collection of cord blood and placental tissue									X	
Labor and delivery documentation ⁵									X	
Standard Care										
Obstetrical exam ⁶	X	X	X	X	X	X	X	X	X	X
Syphilis screening	X									
Iron and Folic Acid	X	X	X	X	X	X	X	X		
Prenatal vitamins	X									
Mebendazole ⁷			X							
Screening for non-malarial parasitic infections ⁸			X							
Vitamin A ⁹									X	
Insecticide treated bednet	X								X	

* Only if study subject enrolled prior to 16 weeks gestation; If the woman is enrolled between 18 or 20 weeks, then the week 20 phlebotomy will not be performed.

Explanation of maternal schedule of events

1. HIV test will be done at enrollment and documented. A repeat rapid HIV test will be done at delivery. HIV testing shall be done using standard rapid HIV-testing algorithm.
2. Pregnancy confirmation by positive urine pregnancy test, or confirmed intrauterine pregnancy by ultrasound. A pregnancy test may be skipped if an intrauterine pregnancy has been noted on ultrasound at the screening visit.
3. Ultrasound will be done to confirm intrauterine pregnancy and estimate gestational age at enrollment. See Appendix B for dating criteria.
4. Targeted physical exam will include anthropometric measurements (e.g. weight) and vital signs (i.e. temperature, pulse, and blood pressure). Measurement of height at the enrollment visit only.
5. Labor & Delivery documentation will include: Peripartum history, mode of delivery, Apgar scores (when available), weight, length, and head circumference of the child at birth, approximate gestational age, duration of labor, signs of fetal distress (presence of meconium), summary of events in first days of life (including feeding, breathing patterns,

jaundice, lethargy, or any additional abnormal findings), duration of admission if delivered in hospital.

6. Obstetrical exam includes estimation of gestational age at study entry, fundal height measurement, fetal heart tones and urine dipstick for protein. A cervical exam will also be performed at screening and during antepartum study visits as clinically indicated.
7. Mebendazole is typically given as 500mg as a single dose as early as possible after the 1st trimester (16 or 20 week visit).
8. Screening for non-malarial parasitic infections will be done prior to administering Mebendazole and will include stool ova and parasite examination, circulating filarial antigens, and blood smear for microfilaremia.
9. Vitamin A supplementation is dosed as 200,000 IU.

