6.5. Routine Assessments

Routine assessments will be done in the clinic every 4 weeks for both pregnant women and children. Study participants not seen in the clinic for their every 4 week routine visits will be visited at home and requested to come to the study clinic as soon as possible. Pregnant women and children will receive standards of care as designated in the Uganda MOH guidelines (Appendix G). Routine antenatal care will include screening and treatment for sexually transmitted Infections, blood pressure assessment, urine dipstick for proteinuria, prescription of iron, folate, multivitamins and mebendazole. Routine care in children will include immunizations, vitamin A supplementation, and management of anemia using Integrated Management of Childhood Illness (IMCI) guidelines. During routine assessments subjects will be asked about visits to outside health facilities and the use of any medications outside the study protocol. The study protocol will be reinforced with discussion regarding the need to come to the study clinic promptly upon the onset of any illness and to avoid use of outside medications. Standardized assessment of adherence will also be done for study drugs administered at home and ITN use. A routine history and physical exam will be performed using a standardized clinical assessment form. Blood will be collected by finger prick (in very young children, heel sticks may be substituted for finger pricks) for thick smear, collection of plasma for PK studies, and filter paper samples. If a pregnant woman or parent/guardian of a child reports a fever in the last 24 hours or the patient has a documented temperature $\geq 38.0^{\circ}\text{C}$ tympanic, the patient's thick blood smear will be read immediately and if positive the patient will be diagnosed and treated for malaria (see section 6.2). Phlebotomy for routine laboratory tests (CBC and ALT) to monitor for potential adverse events from study medications and for immunology studies will be performed every 8 weeks in pregnant women and every 16 weeks in children. Screening for non-malaria parasitic infections will be performed once in pregnant women after the 1st trimester at the time routine mebendazole is administered and in children at 1 year of age.

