6.6. Delivery visit

Addressing one of the main study outcomes, placenta malaria, requires collection and processing of specimens at delivery. Systems will be in place to facilitate a birth plan which will encourage women to come to the hospital for delivery, including access to transportation 24 hours a day. However for women who are unable to travel to the hospital for delivery or choose to deliver at home, a study staff member will be driven to the home to follow study procedures. Study staff will document details of the delivery, including date and time, type of delivery, estimated blood loss and any maternal, obstetrical or neonatal complications. Study staff will document the infant's Apgar score and birth weight with calibrated scales. Biological samples collected at the time of delivery will include maternal venous blood (for thick blood smear, filter paper samples, CBC, ALT, immunology studies, and PK studies), cord blood (for thick blood smear, filter paper samples, hemoglobin measurement, and immunology studies) and placental tissue. Following delivery, neonatal care, as per national guidelines, will include polio and BCG immunization, ophthalmic tetracycline, vitamin K, and vitamin A supplementation.

At the time of delivery, women will undergo repeat rapid HIV testing based on national guidelines. If women are found to have become HIV-infected during pregnancy, both the mother and their newborn will be withdrawn from the study and immediately referred for care following local prevention of mother-to-child transmission (PMTCT) guidelines.

6.7. Postpartum visits.

Women will be evaluated within 1 week following delivery and 6 weeks postpartum as part of routine care. Both visits will include an abdominal exam syndromic management of STIs, and follow-up on any obstetrical complications that occurred including evaluation of the neonate for any congenital abnormalities. Pelvic and breast exam will be done if clinically indicated. Contraceptive counseling, nutritional assessment and infant feeding and support will be provided. Following the 6 weeks visit, women will no longer be considered study participants, although most will remain primary care givers for their children enrolled in the second phase of the study.

Summaries of all procedures done during routine visits in pregnant women and children are presented in Appendix H and I, respectively.

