6.10.2. Clinical Laboratory Studies

At enrollment and every 8 weeks during follow-up for pregnant women and every 16 weeks for children, venipuncture blood samples will be collected for routine clinical laboratory studies, including CBC and ALT measurements. Additional venipunctures will be performed, as appropriate, for laboratory testing to evaluate non-malarial medical illnesses at the discretion of study physicians. Results will be made available to study physicians in a timely manner for patient management decision-making. Additional hemoglobin measurements will be performed each time a patient is diagnosed with malaria using a portable spectrophotometer (HemoCue, Angholm, Sweden) and results will be immediately available.

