6.10.5. Immunology Studies

Venipuncture blood samples collected at enrollment, during routine visits done every 8 weeks in pregnant women and every 16 weeks in children, and in select subjects on the day malaria is diagnosed (above) will be made available for immunology studies. Approximately 15mls of blood in pregnant women and 5mls of blood in children will be collected and separated into plasma and peripheral blood mononuclear cells (PBMC) using a Ficoll gradient, following standard protocols. Plasma will be stored at -80°C for future immunologic, which may include measurement of levels of cytokines, antibodies, and other features related to the host immune response. PBMCs will be stored in liquid nitrogen to maintain viability, and will be evaluated using flow cytometry, ELISPOT, RT-PCT, expression microarrays and other assays to assess the host immune response. Stool will be collected at 1, 2, and 3 years of age in children and evaluated for parasitic infections, and remaining stool will be stored for future studies analyzing the influence of parasitic and bacterial infections on immunity. Information from immunology studies will have no impact on patient care. Immunology studies will be done in Uganda whenever possible. However, due to technological limitations some immunology studies may be done at UCSF.

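### Appendix H schedules maternal CBC/ALT draws at weeks 28 and then 40, a 12-week step, although sections 6.5, 6.10.2 and 6.10.5 set an 8-week interval

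*Protocol*

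**What the plan says.** Three sections of the protocol agree on the interval between maternal blood draws.

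- Section 6.5, on the CBC and ALT tests used to monitor drug safety and on the immunology samples: phlebotomy "will be performed every 8 weeks in pregnant women and every 16 weeks in children".
- Section 6.10.2, on clinical laboratory studies: "At enrollment and every 8 weeks during follow-up for pregnant women".
- Section 6.10.5, on immunology samples: "during routine visits done every 8 weeks in pregnant women and every 16 weeks in children".

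Section 6.7 then refers the reader to the schedules: "Summaries of all procedures done during routine visits in pregnant women and children are presented in Appendix H and I". In Appendix H, the row "Blood collected by phlebotomy for CBC, ALT, and immunology studies" is marked at enrolment, week 20, week 28, week 40 and delivery. Weeks 16, 24, 32 and 36 and the postpartum column are blank. The only footnote on draw timing drops the week-20 draw for women enrolled at 18 to 20 weeks. Section 6.6 confirms the delivery draw, listing "maternal venous blood (for thick blood smear, filter paper samples, CBC, ALT, immunology studies, and PK studies" among the samples taken.

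**The concern.** The text and the table give site staff two different schedules for the same safety bloods, and nothing says which governs. The draws serve two statistical purposes. They are the routine laboratory monitoring for adverse events, on which the section 6.14 rules for holding study drug depend. They also supply the routine haemoglobin values behind the secondary anaemia outcome in Table 7.

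If the table is followed, two groups of women are affected.

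- **Delivery after the week-36 visit and before the week-40 visit.** One routine draw is lost. The anaemia outcome loses a value, and laboratory effects of the week-28 and week-32 courses are first looked for at delivery.
- **Reaching week 40.** No draw is lost, but there is none for 12 weeks, and the week-40 course is given with no CBC or ALT result since week 28. Under the Appendix D table headed "Timing of administration of study drugs during pregnancy", that course is active drug only in the monthly DP arm. Only there could a week-36 result lead to active drug being held at week 40.

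**Working it through.** **Reading the row.** The Appendix H table has ten columns: enrolment, weeks 16, 20, 24, 28, 32, 36 and 40, delivery, and postpartum. The phlebotomy row has ten fields, with marks at enrolment, 20, 28, 40 and delivery.

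**Steps between marked weeks.**
- 28 − 20 = 8 weeks, as the text states.
- 40 − 28 = 12 weeks, against 8.

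**Does any count of 8 weeks give 28 and then 40?**
- From the table's own week 28: 28 + 8 = 36.
- From enrolment at 12 weeks: 20, 28, 36.
- From enrolment at 16 weeks: 24, 32, 40.
- From enrolment at 20 weeks: 28, 36.

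None does. The footnote on week 20 allows a gap of at most 28 − 18 = 10 weeks, early in follow-up, and does not bear on the later step.

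**Effect by time of delivery.**

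| | Table as it stands | Mark at week 36 |
|---|---|---|
| Delivery between the week-36 and week-40 visits: haemoglobin values after week 20 | 28, delivery = 2 | 28, 36, delivery = 3 |
| Delivery at 38 or 39 weeks: longest gap from week 28 | 10 or 11 weeks | 8 weeks |
| Delivery after the week-40 visit: haemoglobin values after week 20 | 28, 40, delivery = 3 | 28, 36, delivery = 3 |
| Reaching week 40: longest gap from week 28 | 12 weeks | 8 weeks |
| Monthly DP, active courses since the last available result when the week-40 course starts | 28, 32, 36 = 3 | 36 = 1 |

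The last row assumes that blood is drawn before dosing and that results do not come back the same day. Section 6.10.2 says only "Results will be made available to study physicians in a timely manner".

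**How many women.** The protocol gives no distribution of gestational age at delivery. As an assumption, take a normal distribution with mean 39 or 40 weeks and SD 1 or 2 weeks. The denominators come from Table 9: 270 women expected with placental outcomes, 90 per pregnancy arm.

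| Mean, SD (weeks) | P(36 ≤ delivery < 40) | of 270 | P(delivery ≥ 40) | of 270 | of 90 on monthly DP |
|---|---|---|---|---|---|
| 39, 1 | 0.840 | 227 | 0.159 | 43 | 14 |
| 39, 2 | 0.625 | 169 | 0.309 | 83 | 28 |
| 40, 1 | 0.500 | 135 | 0.500 | 135 | 45 |
| 40, 2 | 0.477 | 129 | 0.500 | 135 | 45 |

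So about 48–84% would fall in the first group and 16–50% in the second.

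**The case against.** The strongest objection is that everything rests on the horizontal position of one mark in a sparse row of machine-extracted text. A mark displaced by one column, from 36 to 40, would still leave ten fields and an intact delivery mark, so neither the field count nor the delivery mark rules this out. Another sparse row of the same table gives some cause for doubt: the HIV-testing row carries a week-28 mark, while its explanatory note mentions only enrolment and delivery. This stands as a reason for caution and for checking the source first. Against it, the other rows examined have ten fields too, the study-drug marks run from 16 to 40 as expected, and the enrolment, 20, 28 and delivery marks on the phlebotomy row fit the text and the footnote.

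Second, the table does not apply a strict 8 weeks anyway: its footnote accepts up to 10, and for deliveries at 38 or 39 weeks the gap is only 10 or 11. That is fair, but it does not account for 12 weeks. It is also fair that three concordant sections would usually outweigh one cell in a summary. Even so, the visit schedule is what clinic staff are likely to work from.

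Third, the practical consequence is slight. The schedule is common to all arms, so no bias between arms is shown. Clinically indicated tests, haemoglobin at malaria episodes and the delivery draw remain. For women delivering between weeks 36 and 40 there is almost no dosing left to prevent: day 1 of the week-36 course is taken in clinic at that visit, so at most two home doses could be stopped. A week-40 draw gives the same chance for the two home doses of the week-40 course. All of this is accepted.

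Finally, the headcounts are assumption-driven, and 270 is the number with placental outcomes, whereas 300 women are to be enrolled. They indicate scale only.

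**Conclusion.** The inconsistency holds. The text requires 8 weeks between routine maternal draws, and the table gives 12 between weeks 28 and 40. It is a minor point, held with medium confidence because the mark's position needs confirming in the source table.

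The loss is one routine haemoglobin value, and one CBC/ALT check before delivery, for women delivering between weeks 36 and 40. For women who reach week 40 it is a delayed check, with a possible effect on active dosing only in the monthly DP arm. The proportions in each group depend on the assumed delivery-age distribution, and the comparison of 3 courses with 1 depends on results not being available the same day. The primary outcome and the sample size are unaffected.

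**What to change.** Check the phlebotomy row of Appendix H against the source table. If the mark does stand at week 40, move it to week 36, so that the row reads enrolment, 20, 28, 36 and delivery, and leave the week-20 footnote as it is. This keeps the table's own weeks 20 and 28 and restores the 8-week step.

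The cost is one table cell. Women already attend at week 36, so no visit is added. Those who deliver between the week-36 and week-40 visits have one more draw, of about 15 mL by the volume in section 6.10.5. Those who reach week 40 have the same number of draws, with the last antenatal one four weeks earlier.
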